The research pharmacist will receive and manage both the non-biologically active gel (placebo) and the Timoptic-XE®. The pharmacist will compound and dispense the Timoptic-XE® or non-biologically active gel hydrogel for the patients according to the arm to which they have been randomized. She will repackage the medications into identical dispensers with a coded label and will dispense a 12-week supply to each patient according to their individual randomized unique identifier to ensure accurate storage and dispensing records. The un-blinded research pharmacist will keep record of the drug and patient treatment group assignment. Please see the VA Research Pharmacist's letter of agreement to participate as described. For Timoptic-XE® the recommended ocular dosage is 0.25mg/day (1 drop in each eye once a day). The average exposed ocular surface is about 3 cm². Based on the studies using timolol topically for ulcerative hemangiomas and the numerous case studies of topical timolol on chronic wounds, the dosage used in this study will be 3 drops/3cm²/day that is equivalent to 0.75mg/3cm²/day. Depending on

the size of the wound, the research pharmacist will dispense one or two bottles (with either Timoptic-XE® or placebo) for the 12 weeks supply as described in the table below.

Wound size (cm ²)	Number of drops	Timolol dosage (mg/day)	Timolol dosage (mL/day)	Dosage for 12-week supply (ml)	Number of bottles (timolol or placebo) dispensed to patient for 12-week supply (1 bottle = 5ml)
			Note: 1 drop = 0.05 ml		
< 0.5	1	0.25	0.05	4.2	1
> 0.5 - 0.9	1	0.25	0.05	4.2	1
> 1.0 - 1.9	1	0.25	0.05	4.2	1
> 2.0 - 2.9	2	0.5	0.1	8.4	2
> 3.0	3	0.75	0.15	12.6	3

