- If ulcers heal sooner than 12 weeks, the subject will be assessed the following week for a confirmatory visit, followed another week later by a 2nd confirmatory visit. Ulcer healing is defined by 100% epithelialization as determined by the clinician. The subject with healed ulcer will also return for follow-up visits Weeks 19, 23, 27 & 31 (visits 16, 17, 18 and 19).
 - Vapometer recordings will be collected on visits corresponding to weeks 19, 23, 27, and 31 on the newly healed ulcer site, 5 cm away from healed ulcer site. Readings on the contralateral side will also be marked and taken and recorded. **5 recordings for each site will be taken and the average will be documented.

NOTE: if ulceration remains open after the 12th week of application – then will switch back to standard of care and the subject will be followed monthly until completion of the study.

Blood samples will be taken on each subject on weeks 4, 8 and 12 to determine serum Timolol level. We do not anticipate blood levels in our patients to be higher than those seen in patients who receive Timoptic XE® gel for ocular indication (normal range: 0.3-0.5 ng/ml). We will terminate study on patients in whom Timolol level is 0.7 ng/ml or higher.

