4.3.4 Study Endpoint (Visit 14/Week 14)

- Subjects to complete the health-related quality of life survey or the VR-36 Health Survey and the Lower Extremity Functional Scale Outcome Questionnaire.
- Vital signs will be obtained and recorded.
- The ulcer will be assessed – visual inspection – complete ulcer characteristics form (see appendix). Determine if reaches 100% epithelialization determined by clinician.
- If concern for infection, confirmatory bacterial culture will be obtained (deep swab culturette or tissue specimen/biopsy). Radiographical X-rays and blood work (CBC, ESR, CRP, and Chem) may also be performed if deemed necessary by investigator clinician.
- Digital imaging of ulcer location, if remains non-healing then 2 images to be obtained prior to and after surgical debridement.
- Surgical debridement of ulcer if not healed, will be performed using curette or blade and standard therapy.
- Vapometer recordings will be collected on visits corresponding to weeks 19, 23, 27, and 31 on the newly healed ulcer site, 5 cm away from healed ulcer site. Readings on the contralateral side will also be marked and taken and recorded. **5 recordings for each site will be taken and the average will be documented
- Changes in concomitant medications, adverse events, compliance to offloading, will be recorded.

4.3.5 2ND CONFIRMATORY VISIT (VISIT 15/WEEK 15)

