6. STATISTICAL DESIGN

Measures:

Measures will be collected at baseline, weekly thereafter, with primary endpoint of complete healing at Visit 14/Week 14, and final secondary endpoint measurement at Visit 17/Week 31. The ulcer will be assessed weekly and will be treated as described above. A designated inter-observer (blinded to the treatment of the subjects) will regularly review images and physical exam findings to determine primary and secondary endpoints. The following measurements will be taken: size (surface area calculation), photos (digital includes ruler) and complete foot ulcer assessment (description of ulcer/characteristics), before and after debridement. Subjects where ulceration healed earlier than Visit 14/Week 14 will have follow-up assessment one week after healing, a 2nd assessment a week after, then 4 monthly visits at Weeks 19, 23, 27 & 31. If the ulceration healed after 12 weeks, then the subjects will be similarly assessed. The subject with healed ulcer will also return for follow-up visits Weeks 19, 23, 27 & 31 (visits 16, 17, 18 and 19).

During the study, if ulceration appears to be infected as determined by clinical presentation characterized by the presence of two or more signs of inflammation, the clinician will follow the protocol of obtaining wound culture for microbiology, radiographs, blood work (CBC, chemistry panel, sedimentation rate, and C-reactive protein), and treatment immediately with appropriate antibiotics. Subjects with infected ulcers will be withdrawn from study and investigators will be notified. In addition, adverse events will be well documented and treated per protocol, and subjects will be withdrawn from study.

Clinical Outcomes:

- The percentage of subjects that have complete closure of ulceration by Visit 14/Week 14 and Visit 17/Week 31. Complete healing will be defined as full re-epithelialization with no drainage, or callus formation and remains closed after 1 week of wound closure.

- Rate of wound healing to achieve complete closure. Weekly measurements of surface area will be recorded using Silhouette Mobile™ ulcer tracing and surface area calculation.
- A diabetic foot ulcer assessment form will be filled out at weekly follow-up visits, that describes characteristics of ulceration including peri-ulcer erythema, wound margins, fibrin, granular tissue, peri-ulcer pruritus, edema and location, pain, amount of drainage and type, amount of epithelialization, pain level, depth, and bioburden.

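### Serum timolol results trigger termination during the double-blind phase with no stated restriction on who sees them, and the plan names both the clinician and a blinded observer as judge of closure

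*Combined protocol and SAP*

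**What the plan says.** The trial is described as double blinded in the Protocol Summary and in section 4.1.

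On serum levels, section 4.3.3 states: "Blood samples will be taken on each subject on weeks 4, 8 and 12 to determine serum Timolol level". It expects levels no higher than those seen with ocular use ("normal range: 0.3-0.5 ng/ml") and then sets the rule: "We will terminate study on patients in whom Timolol level is 0.7 ng/ml or higher". Timolol serum level is also the primary safety outcome.

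On masking, section 4.2 has the pharmacist repackage both products into identical dispensers with coded labels. It names one un-blinded role: "The un-blinded research pharmacist will keep record of the drug and patient treatment group assignment". The assay results are not routed to that role or to any other.

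On who judges closure, the plan gives two answers:

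- Section 4.3.3: "Ulcer healing is defined by 100% epithelialization as determined by the clinician".
- Section 4.3.4, the primary endpoint visit: "Determine if reaches 100% epithelialization determined by clinician".
- Section 6, Measures: "A designated inter-observer (blinded to the treatment of the subjects) will regularly review images and physical exam findings to determine primary and secondary endpoints".

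No passage says which judgement counts if the clinician and the observer differ.

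**The concern.** The termination rule can work only if someone reads individual levels while treatment is still running. The control is a gel without active drug, so a measurable level is strong evidence of allocation to timolol. The coded dispensers close one route to the allocation, and the assay opens another that the plan does not close.

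Closure is a visual and bedside judgement. It requires re-epithelialization, no drainage and no need for a dressing. If the person making that call, or recording the exam findings behind it, knows the level, the call can drift with the arm.

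So can care that affects healing and retention: debridement, offloading advice, and the investigator's discretion under section 3 (Withdrawal) to discontinue a subject judged not to have responded. A blinded image reader cannot undo those differences. With 24 subjects per arm, a few judgements are enough to matter.

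**Working it through.** **1. The plan's own figure.** Inputs from section 6, Sample Size Estimation: 20% closure on control, 63% on timolol, two-sided Fisher's exact test at 5%, 80% power, 24 per arm. Exact enumeration, rejecting when p ≤ 0.05, gives power of 79.5% at 23 per arm and 82.5% at 24. The stated 24 per arm is reproduced.

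**2. The documents side by side.**

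| Question | What the plan gives |
|---|---|
| Who is sampled, and when? | Every subject, weeks 4, 8 and 12 (4.3.3) |
| Who receives the results? | Not stated |
| Who applies the termination rule? | An unnamed first-person plural (4.3.3) |
| Who is named as un-blinded? | The research pharmacist only (4.2) |
| What is the expected level on placebo? | Not stated |
| What is the assay detection limit? | Not stated |
| Who determines closure? | The clinician (4.3.3, 4.3.4); the blinded observer (6, Measures) |
| Who records the exam findings the observer uses? | Not stated to be masked staff |

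**3. How far a few calls could move the result.** The plan has no figure for this, so the miscall rate is an assumption. Let p be the true closure rate on timolol and m the fraction of unhealed timolol ulcers scored as closed. Only unhealed ulcers can be miscalled this way, so

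observed rate = p + m(1 − p).

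- With p = 0.20 and m = 0.10: 0.20 + 0.10 × 0.80 = 0.28. This is a shift of 8 points, or 24 × 0.08 ≈ 1.9 subjects.
- With p = 0.63 and m = 0.10: 0.63 + 0.10 × 0.37 = 0.667. This is a shift of 3.7 points, or 24 × 0.037 ≈ 0.9 subjects. It is 3.7/43 ≈ 9% of the design difference.

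**4. Effect on the primary test if there is no true difference.** Set true closure at 20% in both arms with 24 per arm. The probability of a significant result favouring timolol is the sum, over all pairs (a, b) with a > b and Fisher p ≤ 0.05, of Bin(a; 24, observed rate) × Bin(b; 24, 0.20).

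| m (assumed) | Observed timolol rate | Chance of a significant result favouring timolol |
|---|---|---|
| 0 | 20% | 1.3% |
| 5% | 24% | 2.9% |
| 10% | 28% | 5.7% |
| 15% | 32% | 9.9% |
| 20% | 36% | 15.9% |

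The benchmark in one direction is 2.5%. Fisher's test starts below it at 1.3%, and a 5% miscall rate is enough to pass it. The table assumes that every miscall reaches the primary analysis.

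**The case against.** The strongest answer is in section 6. The blinded observer is there to determine the primary and secondary endpoints, and complete healing must also persist for one week. Both would filter out some clinician errors. The sentence in section 4.3.3 about the clinician sits beside the scheduling of confirmatory visits and can be read as a visit-management rule. The routing of results might also be set in the pharmacist's letter of agreement or in a DMC charter, neither of which is reproduced.

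Much of this stands. A reader might infer that the blind is simply unprotected for the primary endpoint, but section 6 does not support that. A reader might also infer that investigators see every level and so know all 48 allocations from the first sample. The documents name no recipient and give no turnaround time.

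Nor do they say that placebo levels are zero. Current ocular or oral timolol use is not a listed exclusion, so a measurable level need not mean the timolol arm. With no detection limit given, an undetectable level need not mean placebo.

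The objection does not remove the gap. The observer relies on exam findings as well as images, and nothing says that those findings come from staff without access to levels. Section 4.3.4 governs the primary endpoint visit itself and names the clinician. Neither blinded review nor the one-week requirement protects care and discontinuation decisions made during treatment.

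**Conclusion.** The point holds in a limited form. The plan creates results that are likely to reveal the arm, requires action on them during the double-blind phase, and does not say who sees them. It also gives the closure call to two different people with no order of precedence. Protection of the primary endpoint is incomplete, and the amount of bias cannot be estimated from the documents.

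The illustration shows sensitivity and is not a prediction. At a 10% miscall rate among unhealed timolol ulcers, closure moves 8 points if true closure is 20% and 3.7 points if it is 63%. With 20% true closure in both arms, the chance of a significant result favouring timolol rises from 1.3% to 5.7%. A reader might expect one miscall in ten to move closure by 10 points, but that would count ulcers that have already closed. These figures assume that the assessor knows the arm, errs in one direction only, and is not corrected by blinded review.

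This should be corrected. It does not invalidate the design.

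**What to change.** 1. In section 4.3.3, state that serum timolol results go only to the un-blinded research pharmacist and the DMC. They apply the plan's existing limit and promptly send the site a stop message that does not contain the level.
2. State that all other site staff have no access to levels until database lock. The planned analysis of serum level against healing can be done after lock.
3. Reconcile sections 4.3.3 and 4.3.4 with section 6. State that the blinded observer's determination is the primary endpoint and that the clinician's call is a sensitivity analysis. State also that the exam findings given to the observer are recorded by staff without access to levels.

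The pharmacist, DMC and observer roles are already in the protocol, so the cost is wording and one relay step. One weakness remains: a stop message triggered by the limit may itself hint at the arm for the few subjects who are stopped. The level at which the rule applies is outside this point and is not questioned.

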4.3.4 Study Endpoint (Visit 14/Week 14)

- Subjects to complete the health-related quality of life survey or the VR-36 Health Survey and the Lower Extremity Functional Scale Outcome Questionnaire.
- Vital signs will be obtained and recorded.
- The ulcer will be assessed – visual inspection – complete ulcer characteristics form (see appendix). Determine if reaches 100% epithelialization determined by clinician.
- If concern for infection, confirmatory bacterial culture will be obtained (deep swab culturette or tissue specimen/biopsy). Radiographical X-rays and blood work (CBC, ESR, CRP, and Chem) may also be performed if deemed necessary by investigator clinician.
- Digital imaging of ulcer location, if remains non-healing then 2 images to be obtained prior to and after surgical debridement.
- Surgical debridement of ulcer if not healed, will be performed using curette or blade and standard therapy.
- Vapometer recordings will be collected on visits corresponding to weeks 19, 23, 27, and 31 on the newly healed ulcer site, 5 cm away from healed ulcer site. Readings on the contralateral side will also be marked and taken and recorded. **5 recordings for each site will be taken and the average will be documented
- Changes in concomitant medications, adverse events, compliance to offloading, will be recorded.

4.3.5 2ND CONFIRMATORY VISIT (VISIT 15/WEEK 15)

4.3.6 Follow-Up Phase (Visits 16 to 19/Weeks 19, 23, 27 & 31)

- The ulcer will be assessed – visual inspection – complete ulcer characteristics form (see appendix). Determine if reaches 100% epithelialization by clinician.
- Digital imaging of ulcer location, if remains non-healing then 2 images to be obtained prior to and after surgical debridement.
- Surgical debridement of ulcer if not healed, will be performed using curette or blade and standard therapy.
- Changes in concomitant medications, adverse events, compliance to offloading, will be recorded.
- Vapometer recordings will be collected on visits corresponding to weeks 19, 23, 27, and 31 ,on the ipsilateral healed ulcer site, 5 cm away from healed ulcer site. Readings on the contralateral side will also be marked and taken and recorded. **5 recordings for each site will be taken and the average will be documented

4.3.7 Real-World Group Phases

Screening/Baseline Period (Visit 1/Week1)

Subjects that meet all criteria of the study will be given an informed consent form to review and sign. Subjects will be required to complete all screening assessments within the 1st visit.

Screening assessments and pre-treatment: A comprehensive history and physical exam along with a battery of tests) will be performed on each study applicant to assess eligibility during the screening phase. Those who do not meet the inclusion criteria and meet any exclusion criteria for the real-world group phase will be excluded.

- 1) Demographic information: gender, age, race.
- 2) Medical history: medical problems, surgeries, trauma, history of previous ulcers, amputations, characteristic and duration.
- 3) Comprehensive history and physical exam: vital signs, height, weight, Body Mass index
- 4) General health and lifestyle: smoking history, alcohol, drugs abuse.
- 5) Lower extremity exam: vascular – pedal pulses, color of skin, temperature, edema; dermatological – clinical description of the ulcer, fungal infection of skin and/or nails, skin integrity (calluses, dryness); musculoskeletal – foot deformities such as bunion, hammertoe, bony prominence, fat pad atrophy, altered gait; neurological – absence or presence of sensation with 5.07/10 Semmes-Weinstein monofilament, reflexes.
- 6) Non-invasive vascular study: ankle-brachial systolic pressure (ABI) and toe-brachial systolic pressure (TBI). In order to meet criteria, ankle-arm index must be equal to or greater than 0.8 and less than 1.4 or a toe-arm index is equal to or greater than 0.6.
- 7) Foot ulcer history (location, length of time, treatments used, pain, etiology of ulcer).
- 8) Laboratory: hematology, chemistry, EKG, microbiology and pathology HbA1c, pregnancy test (for women of childbearing ages), LFT, ESR, CRP and albumin.
- 9) Radiological imaging – plain foot and/or ankle films for baseline.
- 10) Subjects will be given the health-related quality of life survey, VR-36 Health Survey and the Lower Extremity Functional Scale Outcome Questionnaire.
- 11) Sharp debridement of ulcer will be performed per standard method. A small sample will be collected for microbiology (gram stain, cultures/sensitivities, and fungal) and pathology.

- 12) Photographs of ulcer will be obtained before and after debridement using Silhouette Mobile™ ulcer tracing, surface area calculation.
- 13) Dressings applied will include non-adhesive dressing (Adaptic® or Mepitel®) over wound bed, covered by dry dressings.
- 14) Off-loading shoes will be given, modified offloading insert (trilaminar plastazote) as determined appropriate per discretion of clinician.
- 15) Blood will be collected for inflammatory marker analysis.

Follow-Up Phase (Visit 2/Week 6)

Subjects will be evaluated and receive standard of care. Appointments will be made as determined by investigator at each VA facility.

All subjects during this visit will have;

- Vital signs
- Ulcer assessment and measurement
- Lab tests per protocol
- Sharp debridement
 - debrided tissue will be collected and analyzed for molecular markers of inflammatory characterization of wound microbiome.
- Wound cleansing and moist wound healing dressing
- Infection assessment if indicated with confirmatory bacterial culture (deep swab curette, tissue specimen/biopsy), radiographical X-rays and blood work (CBC, ESR, CRP, and chemistry) if deemed necessary by investigator clinician.
- Use of an offloading device that protects the wound from pressure or trauma related to ambulation and other acts of daily living. The total contact cast or instant total contact cast would be ideal offloading devices. However, given the nature and complexities associated with DFU, it is unrealistic to expect that all patients to tolerate such offloading devices. Thus, the offloading device provided will be dependent on the subjects' ability to tolerate the specific offloading device. Adherence to offloading device will be evaluated by the investigator at each visit by observing plantar wear patterns and inquiring from the patient if offloading was used consistently as instructed. Alternative to total contact cast or instant total contact cast (cam walker), offloading devices will be offered including, but not limited to the use of felt/foam adhesive/post op shoe, custom offloading insole, and customized healing shoe in combination with gait assistive device such as a roll-a-bout scooter, walker, wheelchair or motorized scooter.
- Application of treatments:
 - Standard of Care: Application of non biologically active gel (hydrogel as placebo medication), non-adhesive dressing (Adaptic® or Mepitel®), over wound bed, covered by dry gauze dressings
- Offloading devices (see above)
- Changes in concomitant medications, adverse events, compliance to offloading, will be recorded.
- Blood will be collected for inflammatory marker analysis

Study Endpoint (Visit 3/Week 12)

- Subjects to complete the health-related quality of life survey or the VR-36 Health Survey and the Lower Extremity Functional Scale Outcome Questionnaire.
- Vital signs will be obtained and recorded.
- The ulcer will be assessed – visual inspection – complete ulcer characteristics form (see appendix). Determine if reaches 100% epithelialization determined by clinician.
- If concern for infection, confirmatory bacterial culture will be obtained (deep swab culturette or tissue specimen/biopsy). Radiographical X-rays and blood work (CBC, ESR, CRP, and Chem) may also be performed if deemed necessary by investigator clinician.
- Digital imaging of ulcer location, if remains non-healing then 2 images to be obtained prior to and after surgical debridement.
- Surgical debridement of ulcer if not healed, will be performed using curette or blade and standard therapy.
- Changes in concomitant medications, adverse events, compliance to offloading, will be recorded.
- Blood will be collected for inflammatory marker analysis.

5. ADVERSE EVENTS

All adverse events reported spontaneously by the subject/or in response to questioning or observation by the investigator will be recorded.

Reporting of Adverse Events:

The Investigator will be responsible for assessing the relationship of the adverse event to the investigational product, and the seriousness and expectedness of the adverse event at the time of occurrence. All adverse events that occur during the trial will be documented.

AE's/SAE's reported during the study, or SAE's reported within 30 days of the end of the study, should be followed to resolution of the AE/SAE or, within thirty days from the end of the study, a further and final assessment of the outcome should be made. Each AE will be categorized as "serious" or "not serious" based on the definition of an SAE. An SAE is defined as an AE resulting in at least one of the outcomes described in the sections below.

The severity of AEs will be classified as "mild", "moderate", or "severe", based on the following definitions:

- Mild: Awareness of sign, symptom, or event, but easily tolerated; does not interfere with usual daily activities or tasks.
- Moderate: Discomfort enough to cause interference with usual daily activity; may warrant therapeutic intervention.
- Severe: Incapacitating; inability to perform usual activities and daily tasks; significantly affects clinical status; requires therapeutic intervention.

Adverse events will be assigned a relationship (causality) to the study products. The Investigator will be responsible for determining the relationship between an AE and the study product. The

type of event, organ system affected, and timing of onset of the event will be factors in assessing the likelihood that an AE is related to the treatment. Relationship of AEs to study products will be classified as follows:

- Not Related: No relationship exists between the AE and the treatment. The event is attributed to a pre-existing medical condition or an intercurrent event unrelated to the study product.
- Possibly Related: Follows the treatment, but may have developed as a result of an underlying clinical condition or treatments/interventions unrelated to the study product.
- Probably Related: Follows the treatment, but is unlikely to have developed as a result of the subject's underlying clinical condition or other treatment or other interventions.
- Definitely Related: Follows the treatment and physical evidence shows a convincing relationship to the treatment.
- Unknown: Follows the treatment, but unable to determine the relationship to the treatment.

Subject Follow-up:

Subjects who experience an AE will be followed until the AE has resolved, if possible.

Serious Adverse Events:

A serious AE (SAE) will be defined as any untoward medical occurrence that occur after signing the informed consent until the Final Evaluation that:

- Results in death,
- Is life-threatening,
- Requires inpatient hospitalization or prolongation of existing hospitalization,
- Results in persistent or significant disability/incapacity,
- Is a congenital anomaly/birth defect,
- Other (event not covered by SAE categories but in the investigator's opinion, should be considered serious).

Important medical events that may not result in death, be immediately life threatening, or require hospitalization may be considered an SAE when, based upon medical judgment, they may jeopardize the subject and require intervention to prevent one of the outcomes listed above.

Reporting Serious Adverse Events:

The Investigator must report all SAEs (including any subject deaths) occurring during the study (from informed consent until the Final Evaluation). Once the Investigator becomes aware of an SAE, he/she must e-mail (preferred method of communication) or telephone the IRB within 24 hours.

A written report must follow within 48 hours of the time the Investigator learned of the event. This written report must include a full description of the event and all supporting documentation available at that time (e.g., lab reports, electrocardiogram [ECG] reports, etc.). Additional follow-up information must be reported to the Sponsor on the appropriate form as it becomes available and/or upon Sponsor request.

Data Monitory Committee:

A Central Data Monitoring Committees board will be established with Hines VA Hospital, [name].

Consultant Services

[name] (Internal Medicine, Section Chief of Infectious Diseases, Assistant Professor of Medicine at UC Davis Medical Center) will assist in the management of subjects and subject safety.

[name] (Endocrinology, Section Chief of Endocrinology) will assist in the management of patient regarding issues related to diabetic glucose control.

[name] (Cardiology, Section Chief of Cardiology) will assist in the management of patients regarding issues pertaining to blood pressure and pulse monitoring.

Stopping Criteria:

The emerging clinical and safety data will be reviewed during the trial, and as a result of this review it may be necessary to terminate the study before all patients have completed the protocol. In such circumstances subjects will be followed up for safety assessment.

